## 1. Study Protocol

### 1.1 Study aims and design

This study, sponsored by the National Institute of Diabetes and Digestive and Kidney Diseases (NIDDK), aims to optimize online behavioral lifestyle intervention (BLI) by testing whether any of five theory-driven experimental intervention components increase the proportion of individuals achieving a minimum clinically significant weight loss of  $\geq 5\%$  of initial body weight and/or mean weight loss after 12 months of treatment. The rationale and design of the study methods are informed by the 3-Phase Multiphase Optimization Strategy (MOST) framework. Per the MOST Optimization Phase, a factorial experiment will be conducted to determine which, if any, of the experimental intervention components contributes to improved treatment outcomes. Adults with a body mass index (BMI) in the overweight or moderately obese range ( $25-30 \text{ kg/m}^2$ ) will receive the preexisting 12-month Rx Weight Loss (RxWL) and a random combination of 0-5 of the experimental intervention components. A priori optimization criteria will be used to evaluate which, if any, of the experimental intervention components should be included in an optimized RxWL treatment package, which can then be tested in a future randomized controlled trial per the MOST Evaluation Phase. Mediation analysis will also be conducted to determine whether the experimental intervention components exerted their intended effects on their putative behavioral and psychosocial mechanisms, and whether those effects were associated with improved weight loss outcomes. Moderators analysis will explore for whom and under what circumstances the experimental intervention components might have been more or less effective. Assessments of weight and hypothesized mediators will occur at baseline and 3, 6, and 12 months after randomization. The study aims are:

**1.1.1 Aim 1:** Optimize RxWL via a factorial experiment to determine which combination of intervention components maximizes the proportion of participants achieving a  $\geq 5\%$  weight loss and mean weight loss at 12-months.

**1.1.2 Aim 2:** Conduct mediation analysis using proximal outcomes to test hypothesized mechanisms of action and moderator analysis to understand for whom and under what circumstances the interventions are effective.

### 1.2 The RxWL intervention.

RxWL is an automated online BLI that was initially developed to support weight loss in adult primary care patients with overweight/obesity.

All participants begin the program with an automated online “kickoff” session that explains BLI basics including goal-setting and self-monitoring. Participants are encouraged to lose 0.5 kg to 1 kg per week, by limiting energy intake to 1200 kcal to 1500 kcal per week depending on starting body weight, to achieve a total weight loss of  $\geq 10\%$  of starting body weight. Other goals include consumption of a low-fat or Mediterranean diet (decided by the participant) and regular moderate-to-vigorous physical activity (MVPA) with weekly MVPA goals that gradually increase to 150 minutes per week by 3-months and 250 minutes by 12 months.

After the kickoff session, participants are provided with weekly interactive multimedia lessons on key BLI topics for 3 months, followed by 9 months of monthly lessons that are designed to support further weight loss and weight loss maintenance. Lessons highlight strategies from the Diabetes Prevention Program and Look AHEAD trial BLIs, with topics that include consuming a healthy diet, meal planning, building an

exercise habit, restaurant eating, social support, and weight regain prevention, among others. The lessons involve a combination of animated graphical content with voiceover and live action video. The lessons are self-paced and allow participants to explore additional information on key topics of interest (e.g., additional examples of how to calculate the calorie content of various prepackaged foods in a lesson explaining label reading and portion size). Navigation through each lesson is self-paced and they are designed to require about 15 minutes to complete.

In addition to the lessons, participants are asked to self-monitor their total energy intake (kcals), daily MVPA minutes, and body weight for the first 3 months of the program and to enter these data on the RxWL platform at least weekly. They are asked to weigh immediately upon waking in the morning, in light or no clothing, with the scale placed on a hard surface. Participants are given instructions and resources for using paper diaries and online/mobile tracking apps for this purpose. Flexibility in the method of self-monitoring improves the potential for reach and dissemination of the program given that some individuals may not own a smartphone for use with tracking apps and/or may have limited confidence in using tracking apps, a more complex technology. Participants are not encouraged to use one method or app over the others, but if the FitBit app is used for self-monitoring, the data can be shared automatically with RxWL via an application programming interface (API). During the final 9 months of the program, participants are asked to self-monitor for one week per month, coinciding with the provision of the monthly lesson. At the end of each week of self-monitoring, a feedback message is algorithmically generated based on participants' self-reported weight, daily reported energy intake (kcals), and daily reported exercise minutes. The content of the feedback changes weekly and provides encouragement and constructive feedback to support adherence to BLI strategies taught in the lessons. The RxWL platform also contains supplementary printable guides on topics such as eating healthfully on a budget, exercising safely, meal planning, and problem-solving. Finally, reminders to engage with the program are sent weekly to participants who have not logged their self-monitoring data.

### **1.3 Description of the experimental intervention components.**

**1.3.1 Online VR intervention for training in basic behavioral weight loss skills.** Experience Success is a fully automated online based VR intervention for experiential training in basic behavioral weight loss skills. Skills training occurs in virtual environments where challenges typically experienced by individuals losing weight (e.g., selecting from a variety of foods ranging in calories and healthfulness, peer pressure to overeat and be inactive, environmental cues for overeating, common barriers to physical activity) are presented. Participants see VR actors implementing skills, practice skills themselves, and receive praise for successful use of skills. Participants end each session by making explicit plans for real-world skills use. The intervention consists of four modules corresponding to four virtual environments: home, the workplace, the gym, and a party (i.e., a social eating situation). Each module contains about two hours of content, but based on a participant's choices, a single scene playthrough takes about 20 minutes. An example of the challenges faced by users in the home module involves how to prepare and pack a healthy low-calorie lunch before the bus to work arrives. The user is presented with a selection of ingredients, cooking methods, and packaged foods. They then experiment with different combinations that balance caloric content, dietary quality, and preparation time until they finalize a meal, which they then learn to prepare. Experience Success was recently found to enhance 12- week weight loss outcomes of the commercial online Weight Watchers program.

### **1.3.2 Tailored interactive video feedback targeting personalized training in dietary skills.**

Like the existing text feedback that this component replaces, the video feedback is automated and uses the exact same algorithm to assemble an aggregate message of 3-4 pre-recorded video clips (approximately 30 seconds each) that varied each week. Video feedback messages are delivered on-camera by an obesity treatment expert for a more interactive experience and to enhance a sense of human connectedness. Feedback content is nearly identical to the text version but modified for a more conversational tone. At the end of the feedback message, participants are given the opportunity to “interact” by choosing from a predetermined set of situations and behavioral challenges to receive a further refined feedback video. For example, participants may select that they are traveling or have experienced sickness, injury, or a significant life stressor. The corresponding feedback teaches skills such as healthy restaurant eating and stress management. If a participant indicates that they are traveling, they might be encouraged to order smaller portions (e.g., appetizers instead of entrees) at restaurants and look for opportunities to increase physical activity to offset increased intake. Additional feedback given in response to selecting a behavioral challenge generally falls into one of the following categories: behavioral skills to support healthy eating (e.g., meal planning), selecting and preparing healthy foods (e.g., increasing fruits and vegetables, reducing sugary beverage intake), maximizing accuracy of self-monitoring (e.g., portion size estimation), and physical activity adherence (e.g., enhancing motivation, introducing variety). Training in dietary skills is particularly emphasized as it provides a method of improving two key elements that drive the feedback, namely dietary intake and weight change. The options for interactivity are titrated each week to reflect the progressive nature of weight management skills acquisition and complement skills taught in the RxWL video lessons (i.e., more basic skills are emphasized earlier in the program, and more advanced skills later in the program).

### **1.3.3 Tailored interactive intervention to promote structured physical activity.**

This component consists of three parts, including evaluation of physical activity, a tailored physical activity plan, and instructional and educational videos for home-based physical activity. The core RxWL program focuses on eating and dietary behavior in the first two weeks and then targets physical activity behavior beginning in the third week, which involves gradually increasing PA to 150 minutes during the first 3 months, then increasing to 250 minutes by the end of the 12-month program. Core program content focuses on gradually increasing PA to meet overall goals, and involves general suggestions for safely building a PA habit that emphasizes brisk walking (e.g., planning ahead for PA, stretching before and after PA).

Consistent with the core RxWL program structure, in week 3 participants receiving the experimental PA intervention component complete an online evaluation of physical activity, with a focus on time spent in structured MVPA. These data inform a tailored physical activity plan that promotes adding 50min/wk (+10 min/day on 5d/wk) to participants' current level of physical activity each month until participants achieve the national guideline of MVPA for weight loss (250 structured minutes weekly). Participants select their preferred plan (10, 20, 30, 40, or 50 min/day on  $\geq 5$  days weekly) for the upcoming four weeks. If participants feel strongly that their suggested goal is not appropriate for them, they can select a different goal (e.g., to push themselves harder or select a lower activity level). The physical activity evaluation, generation of the tailored activity plan, and delivery of tailored video content reoccurs after two weeks, and monthly thereafter for the duration of their participation.

Participants are given long-form exercise videos to complete at home. To ensure that participants have appropriate support for each of the physical activity goals they could select during the evaluation and

planning step, videos are available with durations of 10, 20, 30, 40, and 50 minutes. The complexity and intensity of the videos increases slightly with duration, but all videos are designed to produce MVPA. Videos primarily utilize body weight exercises targeting all muscle groups and increasing heart rate. Each exercise is presented with modifications for adaptation to the participant's functional capacity, preexisting injuries, and movement preferences. All the exercises can be done within a 3'× 2' space. No equipment is needed for most exercises, but a mat and light hand weights are utilized in some adaptations. Participants are given guidance on safety, avoiding injury, and alternatives to hand weights that they may use if desired. Most of the exercises are conducted over a time interval (e.g., "Do this exercise for 45 seconds") so that participants do not need to count repetitions and sets of weight-bearing exercises. Each video includes background music, narration, and instructors synchronously demonstrating the same exercise from different views and/or at different ability levels. When the PA goal is selected, all videos at that duration and lower are made available to allow flexibility in meeting the goal (e.g., at participant with a 40 min/day goal may choose to do the 20 minute video twice in a day if they find it difficult to set aside 40 uninterrupted minutes for physical activity).

Participants are provided with supplementary videos each month in addition to the long- form videos. The topics are primarily instructional (e.g., upper body exercises, lower body exercises, warming up and cooling down, core mat work) or educational (e.g., overcoming exercise barriers, converting intentions into actions). Participants setting a higher MVPA goal (based on recent MVPA engagement) receive additional videos to facilitate additional optional strength training and exercise of higher intensities. Participants are instructed to count sets and repetitions (or use time goals when appropriate) and determine the appropriate supplementary weight needed. They are also given injury prevention information, tips for proper form, and suggestions for modifying the 10-50 minute videos to increase intensity. These videos are not made available to participants selecting a lower minute goal in order to avoid overwhelming them and to focus them on building an initial physical activity habit. Participants may access the supplementary videos available to them as often as they like.

**1.3.4 Tailored interactive skills training to address dysregulated eating.** This component consists of interactive skills training videos (i.e., "modules") that utilize ACT approaches to target the impact of dysregulated eating on weight loss. The ACT strategies are presented as compatible with the "control" and "change" strategies that are taught much more briefly in the core RxWL program; participants are encouraged to use ACT strategies when they find that the strategies taught in the core program are insufficient for addressing dysregulated eating. Starting in week 4, participants complete an evaluation to identify negative internal experiences (i.e., thoughts, feelings, and bodily sensations) that can trigger dysregulated eating by rating statements on a 5-point Likert scale (e.g., "When I'm upset, I use food to make myself feel better", "I need to have fewer food cravings in order to succeed with my weight management", "Excuses often get in the way of me meeting my health goals"). An algorithm then generates suggestions for modules to be completed based on participant responses and provides a brief summary of the content of each module. The participant selects a module, which consists of four consecutive weeks of 20-minute video lessons with assignments to practice skills in between sessions. There are four modules: 1) the "Cravings" module uses guided-meditation exercises to teach craving awareness and tolerance (i.e., the ability to non-judgmentally observe cravings without eating to make them go away); 2) the "Thoughts" module uses metaphors and experiential exercises to help participants recognize patterns of difficult thoughts and learn alternative strategies for coping with them (e.g., non-judgmental acceptance); 3) the "Acceptance" module uses metaphors and guided-meditation exercises to illustrate the consequences of trying to control emotional experiences (e.g., using eating to change negative emotions) and presents an alternative: being willing to feel undesirable emotions in the service

of staying on track with one's health goals; and 4) the "Motivation" module uses experiential exercises to clarify participant values and explicitly link these values to RxWL program goals (i.e., reducing calorie intake, improving diet quality), and then teaches strategies to strengthen commitment to one's chosen values. The dysregulated eating evaluation and tailored suggestion process repeats monthly.

**1.3.5 Online platform for social support and friendly competition.** This component provides participants with the opportunity to post messages to each other in a shared public form. Conversation threads allow for in-depth conversation and discussion, while a Twitter-like feed allows participants to post short messages and questions. Participants may also create a profile, including a photo, their first name (or a preferred nickname to maintain anonymity), and a brief message about interests, preferred weight loss strategies, and challenges. Participants will be discouraged from discussing their experiences with the other experimental intervention components on the public form in order to limit risk of contamination between conditions. Communication in the online forum will be monitored and participants will be asked to remove any mention of other experimental intervention components, should they be posted.

Friendly competition, accountability, and recognition of success are facilitated by a leaderboard for weekly/total weight loss, weekly/total MVPA minutes, and longest streak of days for self-monitoring. The top 10 participants' first name or nickname is displayed. Participants are also awarded badges that are displayed on their profile when they accomplish important milestones. Some can be reached quickly, such as losing the first 5 lbs., self-monitoring daily for a full week, and exercising for  $\geq 50$  mins within a single week. Conversely, some milestones require weeks or months to achieve, such as reaching a 5% and 10% weight loss, self-monitoring daily for a month, and exercising for a total of 5,000/10,000 minutes. When a new badge is earned, the participant receives an online notification.

#### **1.4 The factorial experiment.**

All participants in the proposed randomized experiment will receive access to 12 months of the RxWL intervention and in addition will be randomized to receive 0-5 of the experimental intervention components, using a full factorial design (Table 1). The majority of participants (63%) will receive two or three intervention components, 16% will receive one or four components, 3% will receive zero or five components. Importantly, each intervention component has been designed explicitly such that receiving any of the other intervention components is neither required nor precluded to fully experience the intervention component and obtain its full benefit. The full factorial design will allow tests of whether there are interactions between components in their effect on weight loss such that certain combinations produce an effect that is stronger or weaker than would be expected given the strength of the main effects.

**1.4.1 Participant eligibility criteria.** Eligibility criteria are kept broad in order to select a sample representative of the target audience for dissemination of RxWL. Inclusion criteria include age 18 to 70 years old; BMI 25-50 kg/m^2; access to the Internet; an ability to walk two city blocks without stopping; and English fluency and literacy at the 6th grade level. Exclusion criteria include current participation in another weight loss program; current use of weight loss medication; weight loss of  $\geq 5\%$  of body weight in the previous 6 months; history of bariatric surgery; pregnancy within the previous 6 months; a plan to become pregnant within 12 months; report of a heart condition; chest pain during periods of activity or rest in the previous 6 months; loss of consciousness in the previous 6 months; report of a medical condition that could make participation in unsupervised physical activity unsafe; or report of a condition that would result in an inability to follow the study protocol including terminal illness, substance abuse, an eating disorder not including Binge Eating Disorder, and untreated major psychiatric illness.

**1.4.2 Participant recruitment and enrollment.** Participants will be recruited via advertisements in local media (e.g. newspapers, radio); targeted online advertising (e.g., Facebook, Google AdWords); flyers and advertisements posted in waiting rooms and exam rooms in primary care offices used in previous studies of RxWL; informational materials made available as part of the health and wellness program for employees in the Lifespan Heath System and hospital network (an approach used in a previous RxWL trial); and direct mailings. A screener completed online or by phone will be used to determine initial eligibility. Individuals who appear eligible will be invited to attend an orientation session at the research center. The study will be described in detail and participants will have the opportunity to complete informed consent, begin the baseline assessment, and schedule their randomization visit. Participants are required to complete the baseline assessment, including wearing the physical activity monitor and completing dietary recalls (described below), to be eligible for randomization.

**1.4.3 Randomization.** Prior to enrollment, a randomization schedule will be prepared based on 12 blocks of 32 patterns of assignment to each of the five intervention components. A sequentially-numbered sealed envelope containing the assignment will be opened by research staff at the time of randomization. The participant will receive brief written materials explaining their assignment and how to begin treatment via the online system. Further orientation to the treatment system is conducted online via interactive video lesson. Study staff will be available by phone to trouble-shoot technical difficulties, but no human-delivered weight loss counseling will be provided in-person or by phone. Participants will be enrolled until the total N=384 target enrollment has been satisfied.

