## 1.6 Statistical Analysis Plan

**1.6.1 Analytic plan.** Statistical analysis will follow good practices for the evaluation of randomized controlled trials as embodied in the CONSORT statement. Missing data will be imputed using a multiple imputation approach and outcome models averaged across imputations to adhere to the intent-to-treat principle. We will compare the sensitivity of the findings to alternative methods for handling missing data (see Missing Data Section below).

As a preliminary step, demographics, baseline weight and health history will be summarized across the aggregate sample and compared between cells (intervention components) using Analysis of Variance (ANOVA) for continuous variables, chi-squared analyses for categorical variables and non-parametric tests as appropriate. Variables will be considered potential confounders in the subsequent models if these variables are correlated with the outcome under consideration (at a modest  $p < .30$  level). The distribution of each of study outcome will be assessed using both parametric and graphical methods and transformed as necessary (e.g. log transform towards normality). Potential distributions for the outcome variables

include normal and binomial, and zero-inflated distributions.

Evaluation of the intervention components will involve generalized linear models that regress percent weight change from baseline (e.g., normal distribution & identity link function) and achievement of a  $\geq 5\%$  weight loss (binomial distribution & logit link function) on effect-coded indicators for each of the five intervention components and unique 2 through 5-way interactions of components. Effect coding  $(-1,1)$  is essential in analyzing factorial designs and results in regression weights that correspond to main effects and interactions.

Effect-coded main effects and interactions are orthogonal to one another, yielding unbiased estimation of standard errors, and equal power for main effects and interactions for given effect sizes. Using this approach, individual cell sizes (for each combination of components) does not limit statistical power. Models will adjust for confounders identified during preliminary analyses, including demographics, health and weight history that are associated with weight loss outcomes.

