**1.6.3 Sample size and power estimates.** Following the full factorial design, each of the planned 384 participants is randomly assigned to each of the five intervention components. There are 32 possible combinations of intervention components, but each component will be administered to 192 persons and withheld from 192 persons. Using the generic approach described by Lehr, a sample size of  $n = 192$  per group permits the detection of standardized effect sizes (SEs) of  $\Delta = (4/n^{.5})$  (where 4 encompasses standard assumptions of a type-I and type-II error rate of  $\alpha = .05$  and  $\beta = 20\%$ , respectively where  $4 \approx \sqrt{2} \times (|z\alpha/2 + z\beta|)$ , and solves to  $SE = 0.29$ ). According to estimates based on our preliminary data, RxWL without additional intervention components produces  $\geq 5\%$  weight loss for 50% of the sample, and the standard deviation on percent weight change will be 5.8% at 12-months. This generic approach estimates power to detect intervention component effects of 9% on proportion achieving  $\geq 5\%$  weight loss and effects of 1.7% on mean weight loss. Statistical power was further evaluated using Monte Carlo estimation, the model specification (with effect coding) for the proposed study, and parameter estimates based on previous RxWL trials. This tailored approach yielded estimates of 91% power to detect a component marginal effect size of  $ES = 0.16$  or an additional 3% achieving  $\geq 5\%$  weight loss and just under 1% additional weight loss due to component effects. The study is adequately powered because a lesser effect would not be clinically significant.

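### The trial randomizes in 12 complete blocks of 32, but the percent-weight-loss model has no block term; if blocks differ, its standard errors are slightly conservative.

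*Combined protocol and SAP*

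**What the plan says.** Section 1.4.3 (Randomization) states that "a randomization schedule will be prepared based on 12 blocks of 32 patterns of assignment". It adds that "A sequentially-numbered sealed envelope containing the assignment will be opened by research staff at the time of randomization" and that "Participants will be enrolled until the total N=384 target enrollment has been satisfied". I read this as 12 blocks that each contain all 32 component combinations once. That agrees with 12 x 32 = 384 and with section 1.6.3, where "each component will be administered to 192 persons and withheld from 192 persons". Because the envelopes are used in order, block number follows enrollment time.

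Section 1.6.1 (Analytic plan) regresses percent weight change (identity link) and achievement of at least 5% loss (logit link) "on effect-coded indicators for each of the five intervention components" and on all two- to five-way interactions. Covariates are added if they are associated with the outcome at p < .30; the examples are demographic, health and weight-related variables. Block, enrollment date and enrollment period are not named, and no reason is given for leaving block out.

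**The concern.** Block is part of how treatment is assigned, so the analysis would normally reflect it. In each complete block, 16 participants receive a given component and 16 do not, and the same balance holds for every interaction. A difference in average outcome between blocks therefore cancels out of every component estimate. It does not cancel out of the residual mean square of a linear model without block. The reported standard error then includes variance that the design has already removed.

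Section 1.6.1 relies on the orthogonality of effect-coded terms for unbiased standard errors. Orthogonality protects the estimates. Under blocked randomization without a block term, the linear model's standard error is on target only if blocks do not differ. Calendar trends, or a changing mix of recruits over the enrollment period, could make them differ.

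What is at stake is a small loss of power. The trial chooses which components to keep, so a missed effect can mean that a useful component is dropped.

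**Working it through.** **Inputs from the documents.** 12 blocks of 32 and N = 384 (section 1.4.3); 192 with and 192 without each component, two-sided alpha of .05 and 80% power (section 1.6.3); "the standard deviation on percent weight change will be 5.8% at 12-months"; detectable "effects of 1.7% on mean weight loss". The full model has an intercept and 31 component terms, leaving 384 - 32 = 352 residual degrees of freedom. With 11 block terms, 352 - 11 = 341 remain.

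**The plan's own figure.** 4/sqrt(192) = 0.2887, which rounds to the stated 0.29. Then 0.2887 x 5.8 = 1.67 points, which rounds to the stated 1.7. Both reproduce.

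**Input that is assumed.** r = s_b²/(s_w² + s_b²), where s_b² is the between-block variance, s_w² the within-block variance, and their sum is 5.8². The documents do not give r, so I use 0, 2, 5 and 10%.

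**True standard error of a component's mean difference.** Block effects cancel, so it is sqrt(s_w² x 2/192) = 5.8 x sqrt(1-r) x sqrt(2/192).

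**Standard error reported without block.** The expected residual mean square is [341 s_w² + 11(s_w² + 32 s_b²)]/352. Since 11 x 32 = 352, this equals s_w² + s_b² = 5.8². The reported standard error is therefore 5.8 x sqrt(2/192) = 0.592 at every r, and the ratio of reported to true is 1/sqrt(1-r).

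**Size and power.** The critical values are 1.9667 (352 df) without block and 1.9669 (341 df) with block. Power is at 1.67 points, from the noncentral t with block, and allowing for the mixed residual mean square without it.

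| Assumed r | SE without block | SE with block | Without block, too large by | Test size without block | Power without block | Power with block |
|---|---|---|---|---|---|---|
| 0% | 0.592 | 0.592 | 0% | 5.0% | 80.5% | 80.5% |
| 2% | 0.592 | 0.586 | 1.0% | 4.8% | 80.8% | 81.3% |
| 5% | 0.592 | 0.577 | 2.6% | 4.4% | 81.1% | 82.5% |
| 10% | 0.592 | 0.562 | 5.4% | 3.9% | 81.8% | 84.4% |

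The method of approximation moves the size and power entries by about 0.1 point. Power without block rises with r because the total SD is held at 5.8, so the true sampling variance falls.

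**Simulation check, linear model** (12 x 32 design, full 32-term model, 20,000 runs per setting). At r = 5% without block, the mean reported standard error was 0.592 against an actual spread of 0.576 under the null, and test size was 4.4%. With block, the reported standard error was 0.577 and size was 4.9%. For an effect of 1.7 points, power was 82.2% without and 83.3% with block.

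**Simulation check, logit model** (main effects only, fixed block indicators, 2,000 runs per setting). At r = 5% and an effect of 1.7 points, adding block raised the standard error of the log odds ratio from 0.207 to 0.214 and the estimate from 0.473 to 0.503. Power went from 63% to 67%. Part of that gain also appears at r = 0 (62% to 65%), where the test with block was slightly liberal (size about 5.8%).

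**The case against.** The case against acting is substantial, and most of it limits the point rather than removing it.

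- **The effect is conditional.** A reader might infer that the standard errors are simply too large. The documents give no between-block variance. At r = 0 nothing is lost, and nothing in the documents supports the 10% row in particular. This stands.
- **Seasonal weight change is a poor reason.** A reader might expect a yearly cycle in body weight to create block differences. The Aim 1 outcome is loss at 12 months from each participant's own baseline, so both weights fall at about the same time of year and such a cycle largely drops out. This stands.
- **Forum activity is a poor reason.** Only participants assigned the social-support component have the forum (section 1.3.5). Variation in it over time would be largely a block-by-component interaction, which an additive block term captures only in part. This stands.
- **Recruitment source is not tied to block.** Section 1.4.2 lists several channels without saying that they are staggered. A change in recruitment over time is possible, but not documented.
- **The logit model behaves differently.** A reader might carry the standard-error claim over to the outcome of at least 5% loss. It does not carry over: adding block there raises the log odds ratio and its standard error together, and the odds ratio becomes conditional on block. This stands.
- **Block is not excluded.** The p < .30 covariate rule is open-ended, so block could enter. That is true, but a factor fixed by the design should be prespecified and not left to a screen on the outcome data.

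Nor does the omission produce bias or an inflated type I error. In the linear model, test size stays at or below 5%.

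**Conclusion.** The point holds as a minor efficiency matter for the percent-weight-loss model. The trial randomizes within complete blocks filled in enrollment order, and the planned linear model does not name block. If blocks differ, component estimates remain unbiased and standard errors are conservative by 1/sqrt(1-r). For shares of up to 5%, that means a standard error no more than 2.6% too large and a power loss of about 1.4 points at most. At an assumed 10%, the figures are 5.4% and about 2.6 points.

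This rests on four assumptions: r, which the documents do not give; the planned SD of 5.8 as the total SD; complete blocks, with every randomized participant's outcome observed or imputed; and block effects that are the same for all component combinations. No conclusion about standard errors is drawn for the logit model.

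**What to change.** In section 1.6.1, prespecify block in the percent-weight-loss model, either as 11 fixed terms or as a random intercept, and say which. In section 1.6.2, include block in the imputation model so that it agrees with the analysis model.

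Block need not be added to the logit model of at least 5% loss. If it is added, the plan should state that the reported odds ratio is conditional on block.

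The cost is a sentence or two in the plan, one more factor in the imputation model, and 11 of 352 residual degrees of freedom. If blocks do not differ, the critical value moves from 1.9667 to 1.9669 and the power loss is negligible (0.03 points or less). Design, sample size and conduct are unchanged.
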